4 STUDY DESIGN

As this is a non-interventional study, the decision to prescribe the product must be taken prior to, and independently from the decision to enrol the participant. This decision should be made in accordance with the Summary of product characteristics (SmPC) and routine/standard clinical practice at the investigational site. The clinical justification for prescribing any treatment should be recorded at the outset by the prescribing clinician.

4.1 Overview

This is an international, multicentre, non-interventional, prospective, single-arm study. This study will be conducted in up to 50 centres in Austria and Germany. A total of 150 participants will be included in the study. Participants will be treated and monitored in accordance with usual medical practice during their participation in this study.

The expected duration of the recruitment period will be 18 months. Participants will be followed for a maximum of 18 months (observation period) while they receive cabozantinib as per the SmPC.

Participants prematurely discontinuing cabozantinib (i.e. within the first 15 months of observation period) and initiating a subsequent treatment will be followed up approximately 3 months after the treatment switch to collect effectiveness data for the new LoT. Enrolment in the study is possible if cabozantinib treatment started up to 4 weeks prior to enrolment. The data for Visit 1 will be captured retrospectively and starting at Visit 2 data will be collected prospectively including hrQoL baseline assessment.

To avoid selection bias in participant recruitment, investigators will offer enrolment to all eligible participants consecutively to achieve their recruitment target during a restricted and defined period. This includes patients who have stopped cabozantinib treatment within their first 4 weeks to avoid selection bias. But, if consecutive enrolment is not feasible (e.g. administrative constraints), an alternate enrolment schedule will be permitted and will have to be documented before the first participant is enrolled. The investigators will have to follow the same recruitment pace until achievement of his/her recruitment target.

4.2 **Population Characteristics**

One hundred and fifty (150) adult participants with unresectable or metastatic, well -differentiated epNET and pNET who have progressed following at least one prior systemic therapy other than SSA, and who are prescribed cabozantinib tablets according to the SmPC prior to entry into the study will be included in Austria and Germany.

Further details of the study population are provided in Section 5.

4.3 Study Data Collection

Participants will be treated in accordance with usual medical practice during their participation in this study. No additional assessments or tests will be required by this protocol. This study is non-interventional, thus if some assessments are not routinely performed by the investigator, they will not complete the corresponding sections in the eCRF.

Relevant data collected as part of routine medical care will be captured on an electronic Case Report Form (eCRF). These data will be transmitted to the sponsor for analysis. Data transmitted will be pseudonymized and will be identified by a participant number.

PROTOCOL FINAL V1.0: 30 JULY 2025

PAGE 20/52

4.4 Study Data Collection Flow

As this is a non-interventional study, treatment with cabozantinib, the nature and timing of study visits and assessments, and data collection at each visit will be conducted as per routine/clinical practice at each clinical site and the SmPC for cabozantinib tablets.

The assessments relevant to this study are presented in Table 4-1. No additional assessments or tests will be required for the purpose of this study.

Table 4-1 Data to be collected in the eCRF

	Collection timepoints (visits)									
		EoS Visit								
		Visit 2	Visit 3	Visit 4	Visit 5	Visit 6	Visit 7	Visit 8	Visit 9 ^a	VISIT FU ^b
Collected data	(Day 1)	(Month	(Month	(Month	(Month	(Month	(Month	(Month	(Month	(approximately 3
		1)	2)	3)	6)	9)	12)	15)	18)	months after cabozantinib treat-
										ment discontinua-
										tion)
Signature of informed consent ^c	X		I	informed o	consent mus	t be signed p	prior to any	documentat	ion of data	
Visit Date	X	X	X	X	X	X	X	X	X	X
Eligibility	X	-	-	-	-	-	-	-	-	-
Demographic and baseline characteristics	X	-	-	-	-	-	-	-	-	-
Significant medical and surgical history	X									
NETs diagnosis	X	-	-	-	-	-	-	-	-	-
Prior systemic treatment for NETs	X	ı	-	-	-	-	-	-	-	-
Prior NETs related radiotherapies	X	•	-	-	-	-	-	-	-	-
Prior NETs related surgeries	X	•	-	-	-	-	-	-	-	-
Tumour assessment ^d	Xe			X^f	Xf	Xf	Xf	Xf	Xf	X ^f
ECOG Performance Status	X	X	X	X	X	X	X	X	Xf	X
Cabozantinib regimen ^g	X	X	X	X	X	X	X	X	X	
Clinical characteristics	X	X	X	X	X	X	X	X	X	
NETs biochemical markers	X	X	X	X	X	X	X	X	X	
EORTC QLQ-C30 and QLQ-GINET21	X	$(X)^h$		X	X	X	X	X	X	
Supporting measures ⁱ	X	X	X	X	X	X	X	X	X	
Concomitant medication for NETs (including concomitant med-	X	X	X	X	X	X	X	X	X	X
ications for AEs)	Λ		Λ	Λ	Λ	Λ		Λ	Λ	Λ
Concomitant non-drug NETs therapy		X	X	X	X	X	X	X	X	
Post-cabozantinib treatment for NETs ^j	-	-	-	-	-	-	-	-	-	X
AEs and Special Situations	X	X	X	X	X	X	X	X	X	X ^k
Study Discontinuation/Completion	-	- X								
Death information form	- X									

Abbreviations: AE=Adverse Event; CR=Complete Response; DCR=Disease control rate; ECOG=Eastern Cooperative Oncology Group; eCRF=electronic Case Report Form; EORTC=European Organisation for Research and Treatment of Cancer; EoS=End of Study; FU=Follow-Up; HrQoL=Health-related Quality of Life; NETs=Neuroendocrine tumours; PD=Progressive Disease; PR=Partial Response; PSP=Patient Support Program; QLQ-C30=Core Quality of Life Questionnaire; QLQ-GINET21= Quality of Life Questionnaire module for GI-NET patients; SD=Stable Disease; TA=Tumour Assessment.

IPSEN GROUP CONFIDENTIAL CONFIDENTIAL

PROTOCOL FINAL V1.0: 30 JULY 2025 PAGE 22/52

All data will be recorded as applicable and available during standard of care routine: if a specific diagnostic procedure is done according to clinical routine the corresponding data should be recorded in the eCRF, otherwise the corresponding part of the eCRF will be marked as not done.

- ^a EoS visit for participants still on cabozantinib treatment after 18 months.
- ^b Combined FU/EoS visit for participants who discontinued cabozantinib early (up to 15 months after Visit 1) and subsequent therapy switch.
- ^c Enrolment in the study is possible if cabozantinib treatment started up to 4 weeks prior to enrolment. See Section 4.1.
- ^d Clinical and/or TA via imaging to determine SD, PR, CR and PD. The type of assessment must be recorded in the eCRF.
- ^e The baseline radiological tumour assessment should be the most recent TA prior to enrolment.
- ^f In case of PD and cabozantinib treatment discontinuation and subsequent therapy switch, only the FU visit must be performed 3 months after end of cabozantinib treatment. Of note, cabozantinib treatment beyond progress is possible; in this case the participant is not passed over to the FU period but remains in the 18-month observation period. In addition, also other reasons e.g. drug intolerability or adverse events might lead to cabozantinib treatment discontinuation and switch to subsequent treatment; in these cases, also only the FU visit must be performed 3 months after end of cabozantinib treatment.
- g Including recording of dose modifications, overdoses, treatment interruptions and permanent study discontinuations along with the reason for discontinuation.
- h Performed if participant was enrolled up to 4 weeks after first dose of cabozantinib and Visit 1 was captured retrospectively. HrQoL baseline will then be taken.
- ¹ Supporting measures include the recording of participation in a PSP, use of psycho-oncological support or nutritional advice.
- ^j In particular, start of new treatment, type of treatment, treatment line and DCR within 12 weeks. For the determination of the DCR after therapy switch, the last TA prior to therapy switch serves as the baseline TA.
- ^k Only AEs related to cabozantinib as assessed by investigator.

PAGE 23/52

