Expected median duration of cabozantinib treatment derives from mPFS in the CABINET trial with 8.4 months for epNET patients and 13.8 months for pNET patients. It is expected that patients visit their physician approximately every 3 months as standard of care. All recruited patients are planned to enter an 18-month observational phase:

- For participants who stop cabozantinib treatment during the first 15 months of the observational period, a follow-up visit will be conducted 3 months after the stop of cabozantinib.
- For participants without discontinuation of cabozantinib, study will be completed after 18 months of observational period.

Study will be conducted from Q4 2025 until Q4 2028.

Recruitment period will be 18 months from Q4 2025 until Q2 2027.

Planned First Participant First Visit: Q4 2025.

Planned Last Participant Last Visit: Q4 2028.

Planned final report: Q4 2029.

Three interim analyses are planned for this non-interventional study:

- 1. Interim analysis 1 (IA1): The first interim analysis is planned to be conducted in Q3 2026, expecting about one third of the target sample size (~50 participants) to be enrolled. It will evaluate data from Visit 1 (Baseline) with a focus on participant characteristics and NETs medical history.
- 2. Interim analysis 2 (IA2): The second interim analysis is planned to be conducted in Q2 2027, expecting about half of the target sample size (~75 participants) to be enrolled. It will evaluate data based on Visit 5 (Month 6) and will focus on effectiveness data, Quality of Life (QoL) and safety.

PROTOCOL FINAL V1.0: 30 JULY 2025 PAGE 5/52

	3. Interim analysis 3 (IA3): The third interim analysis is planned to be conducted in Q1 2028, when full recruitment is expected. Updates on IA2 evaluations will be given as well as analyses on later endpoints and will focus on effectiveness data and post-cabozantinib therapies.							
Study Design:	International, multicentre, non-interventional, prospective, single-arm study conducted at up to 50 sites in Germany and Austria.							
Study Population:	150 adult participants in Austria and Germany who are prescribed cabozantinib tablets for unresectable or metastatic, well-differentiated extra-pancreatic (epNET) and pancreatic (pNET) neuroendocrine to mours who have progressed following at least one prior systemic the apy other than somatostatin analogues prior to entry into the studies will be included.							
	Inclusion Criteria							

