4.5 Study Data Collection Timing and Methods

The expected duration of the study is maximum of 36 months. The expected duration of recruitment is 18 months. Participants will be followed-up for up to 18 months of cabozantinib treatment. If cabozantinib is discontinued during the first 15 months of observation, and a subsequent therapy is started, a follow-up visit will be performed approximately 3 months after discontinuation of cabozantinib. Enrolment in the study is possible if cabozantinib treatment started up to 4 weeks prior to enrolment. The data for Visit 1 will be captured retrospectively. Starting at Visit 2 data will be collected prospectively including hrQoL baseline assessment. Patients who have started cabozantinib treatment up to 4 weeks before giving informed consent but stopped treatment during the 4 weeks may be included.

Three visit types will be performed:

- Baseline Inclusion/ Treatment Initiation Visit (Visit 1)
- Regular visit during the observational period (Visits 2 to 9) approximately every month until Month 3 and every 3 months afterwards
- Follow-up visit for participants discontinuing cabozantinib treatment during the 15-month observational period

All data will be recorded as applicable and available during standard of care routine. If a specific diagnostic procedure or assessment is done according to clinical routine the corresponding data should be recorded in the eCRF, otherwise the corresponding part of the eCRF will be marked as not done / not available.

The timing of the visits according to routine clinical practice is assumed to be close to the proposed schedule. If the timing does not meet the schedule, entries should be made at the visit nearest in time to the proposed schedule.

For regular visits during the observation period the minimum information that must be recorded is the most recent result of the tumour assessment at/before Visit 1 to obtain a baseline value required for determination of the primary endpoint, DCR. Minimum required information for follow up visits after therapy switch, i.e. starting a new LoT includes the start date of new treatment (partial dates are allowed) and the type of treatment.

Adverse events (including treatment-emergent nonserious AEs and serious adverse events (SAEs)) and Special Situations (SS) including pregnancy will be collected during the observation period, see Section 9.

Inclusion/Treatment Initiation (Visit 1)

The following data will be collected:

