4.7 Study Duration/Observation Period

The expected study duration is 3 years, with an 18-month enrolment period from first participant, first visit. The EoS is expected to be a maximum 18 months after the last participant has been enrolled.

The study will be considered to have started when the first participant has signed informed consent.

The study will be considered to have ended after the last participant's data has been collected.

The study observation period starts from participants signing the informed consent and continues until Visit 9 (Month 18). Participants discontinuing cabozantinib treatment and starting a new LoT during the first 15 months of cabozantinib treatment are passing over into the follow-up, which is approximately 3 months after discontinuation of cabozantinib.

Participants will be followed until the end of observational period (i.e. a maximum of 18 months after Visit 1) or withdrawal of consent, or death, whichever occurs first.

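### For stops between Month 15 and Month 18 the closing-visit rules conflict, and a late therapy switch has no assured place to be recorded as a line of therapy

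*Protocol*

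**What the plan says.** Table 4-1 (Section 4.4) has two closing visits. Footnote a makes Visit 9, at Month 18, the "EoS visit for participants still on cabozantinib treatment after 18 months". Footnote b describes the other as "Combined FU/EoS visit for participants who discontinued cabozantinib early (up to 15 months after Visit 1) and subsequent therapy switch". The Synopsis (Study Timelines) makes the same two-way split: anyone stopping by Month 15 has a follow-up visit, while the rule for the rest reads "For participants without discontinuation of cabozantinib, study will be completed after 18 months of observational period".

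Other text does not fit that split. Footnote f, attached to the tumour assessments from Visit 4 on, says that after a stop and a switch "only the FU visit must be performed 3 months after end of cabozantinib treatment"; it carries no Month 15 limit. Section 4.7 runs observation to Visit 9, with a maximum of 18 months after Visit 1, and says that participants who stop and are "starting a new LoT during the first 15 months of cabozantinib treatment are passing over into the follow-up". Section 4.5 counts Visits 2 to 9 as regular visits.

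The row "Post-cabozantinib treatment for NETs" in Table 4-1 is blank at Visits 1 to 9 and marked only in the follow-up column. Section 4.5 likewise lists subsequent treatment only under the follow-up period.

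**The concern.** A participant who stops at Month 16 and starts another therapy at Month 17 gets a different answer from each rule. Sites can resolve this differently, and only one resolution (footnote f) leads to a visit at which the new line is collected.

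The endpoints at stake are secondary: frequency and type of therapy switch, and TTNT. Section 8.4.3.2 summarises TTNT as a quantitative variable in participants with a subsequent therapy. A switch that is not recorded as such is therefore absent from the summary rather than censored. A switch after a stop in Months 15 to 18 has a TTNT of at least about 15 months, so losing it lowers the switch proportion and shortens TTNT.

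**Working it through.** **1. The plan's own figure.** The protocol gives no figure for late stops. Its one precision figure (Section 8.3) reproduces: 1.96 × √(0.7323 × 0.2677 / 135) = 0.0747, or ±7.5%, with 145/198 = 0.7323 and 150 × 0.9 = 135. This point does not depend on it.

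**2. The rules side by side, for a stop at Month 16 and a switch at Month 17.**

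| Text | Visit 9? | Follow-up visit? |
|---|---|---|
| Footnote a | No (not on drug at Month 18) | – |
| Footnote b | – | No (stop after Month 15) |
| Synopsis | No (has discontinued) | No (stop after Month 15) |
| Footnote f | No (follow-up only) | Yes, at Month 19 |
| Sections 4.5 and 4.7 | Yes (observed to Month 18) | No (not within 15 months) |

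Footnote f also collides with Section 4.7. A visit 3 months after a stop in Months 15 to 18 falls in Months 18 to 21, beyond the 18-month maximum.

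**3. Where the switch would be recorded.** If Visit 9 takes place, the regimen page takes the stop date and reason, and a new drug might be entered as concomitant NET medication. The post-cabozantinib row, which holds start, type, line and response of the new therapy (footnote j), is not open at that visit.

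**4. How many stop in the window.** Inputs from Section 2.3: median treatment duration 5.5 months (epNET) and 8.3 (pNET); median PFS 8.4 (epNET) and 13.8 (pNET), which the Synopsis uses for expected treatment duration. Assumption: exponential time on treatment, S(t) = 2^(−t/m) for median m. Fraction stopping in the window = S(15) − S(18). Share of all stops by Month 18 = that fraction / (1 − S(18)).

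| m (months) | S(15) | S(18) | Difference | Of 150 | Share of stops |
|---|---|---|---|---|---|
| 5.5 | 0.1510 | 0.1035 | 0.0475 | 7.1 | 5.3% |
| 8.3 | 0.2857 | 0.2224 | 0.0633 | 9.5 | 8.1% |
| 8.4 | 0.2900 | 0.2264 | 0.0636 | 9.5 | 8.2% |
| 13.8 | 0.4708 | 0.4049 | 0.0658 | 9.9 | 11.1% |

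Mixing the tumour types keeps the result inside this range. A pNET share of 7.3% (Section 8.5) gives 7.3 with the treatment-duration medians and 9.6 with the PFS medians; a share of 64/198 gives 7.9 and 9.6. On 135 participants the range is 135 × 0.0475 = 6.4 to 135 × 0.0658 = 8.9.

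**5. From stops to switches.** For illustration, assume every stopper starts a new line exactly 1 month later. Only stops in Months 15 to 17 then give a switch by Month 18: 150 × (0.1510 − 0.1174) = 5.0 at m = 5.5, and 150 × (0.4708 − 0.4258) = 6.8 at m = 13.8. Deaths, no further therapy and dropout reduce this further.

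**6. Related inconsistencies.**
- The 15 months run from Visit 1 (footnote b), over the observation period (Synopsis, 4.1, 4.5; starting at consent in 4.7) or over cabozantinib treatment (4.7). Enrolment may follow the first dose by up to 4 weeks, so that is the largest difference.
- The Synopsis and the follow-up part of Section 4.5 give follow-up to every stop in the first 15 months. Footnote b requires a switch, as does the opening of Section 4.5: "If cabozantinib is discontinued during the first 15 months of observation, and a subsequent therapy is started, a follow-up visit will be performed". A participant who stops early without switching therefore also fits neither footnote a nor footnote b.

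**The case against.** The strongest reply is that footnotes a and b should not be read alone. A reader might infer from them that a Month 15 to 18 stopper has no closing visit, that a late switch is never recorded, and that the last adverse events on drug are lost. The documents do not support any of these.

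- Footnote f, taken literally, grants a follow-up visit, and Sections 4.5 and 4.7 keep the participant under observation to Visit 9.
- Visit 9 collects the regimen, concomitant NET medication and non-drug NET therapy.
- Adverse event collection is set by Sections 9.2 and 9.2.1, independently of the two footnotes.

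The 15-month limit also looks deliberate. Section 2.3 describes 15 months plus a 3-month follow-up, and Section 4.1 gives the follow-up visit the purpose of collecting effectiveness of the next line, which needs about 3 months on it. The clock difference shrinks further if Visit 1, called the treatment initiation visit in Section 4.5, is taken as the first dose. Finally, finite follow-up would cut off TTNT at some point whatever the footnotes said.

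All of this stands against the absolute reading. It does not remove the conflict: the texts that would rescue the participant contradict each other, and the one that keeps the participant to Visit 9 leads to a visit without the post-cabozantinib row. The purpose of the 15-month limit concerns response on the next line. It gives no reason to leave the start and type of a late switch uncollected.

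**Conclusion.** The point holds as an inconsistency. For stops between Months 15 and 18, footnotes a, b and f, the Synopsis and Sections 4.5 and 4.7 cannot all be followed, and a late switch has no assured place as a line of therapy. Switch proportion and TTNT can be biased downward, and the description of next therapies can omit the latest ones.

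The size is modest: at most about 7 to 10 of 150 participants, or 5% to 11% of stops by Month 18. This rests on exponential time on treatment and on the cited trial's medians applying here. It counts stops, so the number of lost switches is smaller. Some may still be captured, depending on which rule a site follows. The affected endpoints are secondary and descriptive; the 6-month disease control rate, the sample size statement and adverse event collection are untouched. The low cost of correction is the main reason to act.

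**What to change.** - **Footnote a:** state that Visit 9 is the closing visit for everyone not passed to follow-up through a stop by Month 15, including those who stop in Months 15 to 18.
- **Table 4-1:** mark the post-cabozantinib row at Visit 9 for participants who have stopped, with at least start date and type of the new therapy.
- **Footnote f:** limit it to stops up to Month 15, so that it agrees with footnote b and places no visit beyond the 18-month maximum in Section 4.7.
- **Clock:** use one time origin for the 15- and 18-month limits in the Synopsis, Sections 4.1, 4.5 and 4.7 and footnote b.
- **Follow-up condition:** say once whether a switch is required, and align the Synopsis, Section 4.5 and footnote b.

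The cost is footnote wording and one eCRF form opened at an existing visit. No visit is added and the planned last visit does not move. Late switchers will have under 3 months on the next line, so they add to switch and TTNT data but not fully to the next-line disease control rate. TTNT will still be cut off at the end of observation.

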6.1.1 Primary Effectiveness Endpoint

Disease control rate (DCR):

DCR is defined as proportion of participants who within 6 months achieve complete response (CR), partial response (PR) or stable disease (SD) determined based on radiographic assessments between the date of the first dose of cabozantinib until the date of progressive disease (PD) or date of subsequent therapy.

Disease response definitions:		
CR	Complete response	Complete resolution of all visible disease.
PR	Partial response	Partial reduction in size of visible disease in some or all areas without any areas of increase in visible disease. Captures a decrease in disease volume even though disease is still present.
SD	Stable disease	No change in overall size of visible disease. Also includes cases where some lesions increased in size and some lesions decreased in size.
PD	Progressive disease	Increase in visible disease and/or presence of any new lesions. Includes cases where the clinician indicates PD or progression of disease as the overall assessment.

Table 6-1 Disease response definitions

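### The baseline tumour scan is tied to enrolment, which may follow first dose by up to 4 weeks, so an on-treatment scan can become the baseline for DCR and ORR

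*Protocol*

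**What the plan says.** **Baseline.** Table 4-1, footnote e: "The baseline radiological tumour assessment should be the most recent TA prior to enrolment". Section 4.5 sets as required information "the most recent result of the tumour assessment at/before Visit 1 to obtain a baseline value required for determination of the primary endpoint, DCR". The Visit 1 list in Section 4.5 asks for the date and type of the last imaging and does not require it to precede treatment.

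**Enrolment.** Section 4.1: "Enrolment in the study is possible if cabozantinib treatment started up to 4 weeks prior to enrolment". On consecutive recruitment it adds: "This includes patients who have stopped cabozantinib treatment within their first 4 weeks to avoid selection bias". For late enrolees, Section 4.5 says: "The data for Visit 1 will be captured retrospectively".

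**Endpoint.** Section 6.1.1 defines DCR from responses "determined based on radiographic assessments between the date of the first dose of cabozantinib until the date of progressive disease" or subsequent therapy. Section 8.4.3.1 puts in the numerator participants with disease control on any assessment after baseline, and in the denominator those in the full analysis set (FAS) with one or more such assessments. A secondary analysis divides by the whole FAS. Section 8.4.3.2 treats ORR the same way.

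**Comparator.** For the DCR of the next line of treatment, footnote j takes the last assessment before the therapy switch as baseline, so that baseline is tied to the treatment change.

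**The concern.** The endpoint clock starts at first dose, but under footnote e the reference scan is fixed by the consent date. For a participant who consents after starting cabozantinib, these differ by up to 4 weeks. A scan in that gap is on treatment and inside the endpoint window, yet footnote e makes it the baseline, so it cannot also be a post-baseline result.

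Two errors can follow. Progression on the gap scan is not counted as a failure, so DCR comes out too high. Shrinkage already visible on it becomes part of the reference, so a response may later be rated as stable disease and be missed for ORR. Scans this early are more likely than routine ones to be prompted by suspected progression, so the few affected participants would not be a random subset.

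**Working it through.** **1. The rules applied to one case.** Take a participant with first dose on day 0, a scan showing growth on day 21 and consent on day 28, still on cabozantinib.

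- Footnote e: the day-21 scan is the baseline, being the last before enrolment.
- Section 6.1.1: the day-21 scan is inside the DCR window, which opened on day 0.
- Section 8.4.3.1: only assessments after baseline count, so the day-21 scan enters neither numerator nor denominator.
- Section 4.5: if Visit 1 means treatment start, the baseline is instead the last scan before day 0.

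The first and last rules give different baselines, and the protocol has no rule of precedence.

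**2. Whether the data would allow later repair.** Visit 1 requests one imaging date and type. It asks for no response and no earlier scan. Table 4-1 has no tumour assessment at Months 1 and 2; the next is at Month 3. The text list for Visits 2 to 9 does ask for the latest radiographic result before each visit, so a gap scan might be entered at Month 1, but the table does not call for it. If the gap scan is entered as the last imaging, the pre-dose scan is not requested at all. The rule therefore has to be settled in the protocol and eCRF.

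**3. The plan's own figure.** Section 8.3 gives 150 × 0.9 = 135 evaluable and a pooled expected DCR of (51 + 94)/(64 + 134) = 145/198 = 73.2%. The half-width is 1.96 × √(0.732 × 0.268/135) = 7.47 points (7.49 at exactly 73%). The stated ±7.5% reproduces and does not depend on the baseline rule.

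**4. Effect per affected participant (illustration).** Start from 99/135 = 73.3%, with early progression correctly counted as failure. Let k be the number whose gap-scan progression becomes the baseline. The values of k are assumed.

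- (a) Later rated stable against that scan: DCR = (99 + k)/135.
- (b) No later assessment, so they leave the denominator: DCR = 99/(135 − k).
- (c) Later rated as progressed again: still failures, so DCR is unchanged.

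| k | (a) | (b) |
|---|---|---|
| 1 | 74.1% (+0.7) | 73.9% (+0.5) |
| 3 | 75.6% (+2.2) | 75.0% (+1.7) |
| 5 | 77.0% (+3.7) | 76.2% (+2.8) |
| 10 | 80.7% (+7.4) | 79.2% (+5.9) |

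**5. The secondary analysis.** Dividing by the whole FAS returns the type (b) participants as failures. It does not correct type (a), who remain counted as disease control.

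**The case against.** The strongest reply is that the protocol already has a first-dose anchor. Visit 1 is labelled Day 1 and treatment initiation, and is captured retrospectively for late enrolees, so the Section 4.5 sentence can mean the last scan before treatment. That reading is fair, and it rules out describing the protocol as fixing one wrong rule. But footnote e names enrolment, so the conflict stands.

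A second reply is that DCR closes at progression, and participants without prior disease control stay failures even if they later improve. That helps only if progression on the gap scan is recorded, and Visit 1 has no item for it.

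A third is that the treating physician judges response and may compare with the true pre-treatment images whatever the eCRF labels as baseline. This weakens the ORR effect, which is why it is put only as possible. It does not change which assessments are counted.

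A reader might infer more than the documents support:

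- *That PFS is inflated too.* Section 6.1.2 runs PFS from first intake to radiological or clinical progression and does not limit it to assessments after baseline.
- *That the participant who stops before consent is the clearest case.* Section 8.1 requires an intake during the study, Section 8.2 requires treatment within the study, and observation starts at consent (Section 4.7). Such a participant may not be in the FAS. Late enrolees still on treatment are affected either way.
- *That the number can be worked out.* Imaging about every 3 months suggests 28/90 = 31% for a 4-week gap. If 20% to 50% of 150 enrolled late, all at 4 weeks, that gives about 9 to 23 on-treatment baselines. The late share is not in the documents, delays spread evenly over the 4 weeks would halve the count, and scans showing progression would be fewer still.
- *That old pre-treatment scans bias DCR the other way.* The documents give no growth rate from which to show this, and a limit on scan age can be left to the SAP.

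**Conclusion.** The concern holds as a conflict over the reference point of the primary endpoint. Footnote e ties the baseline to enrolment, the endpoint window is tied to first dose, Section 4.5 can be read either way, and no text requires a pre-dose scan. Followed literally, footnote e lets an on-treatment scan, even one showing progression, become the baseline. DCR is then biased upward, and ORR may lose early responses.

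The number affected is probably small and cannot be estimated from the documents. Each early progression lost moves DCR by about 0.5 to 0.7 points, assuming the participant is later rated stable or has no later assessment. Around ten such cases would be needed to approach the 7.5-point half-width. The sample size and stated precision are unaffected. This should be fixed, but it does not undermine the study.

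**What to change.** - In footnote e, the Section 4.5 sentence on the baseline value and the Visit 1 list, define the baseline as the most recent radiological tumour assessment on or before the first dose of cabozantinib.
- State that any scan after first dose, including one before enrolment, is a post-baseline assessment, and record its date and response.
- Add an eCRF check of the baseline scan date against the first-dose date.

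The cost is a few lines of protocol text, a response entry for scans in the gap, and one edit check. No extra imaging is needed, so the study stays non-interventional. The drawback is that a few late enrolees may have no usable pre-dose scan. They should be reported as such and not given an on-treatment baseline.
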